The generic nifedipine ER product which utilizes a different release mechanism could amplify or reduce such a pH dependence (e.g. osmotic pump RLD vs. matrix generic counterparts). Under the existing regulatory practice, ANDA applicants of oral ER drug products are not required to conduct BE studies comparing the generic products with the RLD in patients chronically taking PPIs or with an abnormal gastric pH. This may render these generic ER products more or less dependent on gastric pH modification, commonly occurred in patients taking concomitant PPIs for the treatment of gastric acid-related disorders. It has been noted that PPIs (e.g. lansoprazole, omeprazole, esomeprazole) and PPIs with antacids (e.g. omeprazole/sodium bicarbonate) can drastically elevate the gastric pH, thus potentially changing the equilibrium solubility of co-administered drug substances or altering their release profiles. In the case of nifedipine, clinical studies have shown that in healthy volunteers receiving a single dose of 10 mg nifedipine IR tablets, AUC and C_{max} of nifedipine after pretreatment with omeprazole 20 mg once daily for 8 days were 1.26 and 0.87 times those after pre-treatment with placebo [10-12]. This shows a potential drug-drug interaction between PPIs and nifedipine that is formulated in an immediate-release dosage form.

Whether such a pH-dependent *in vitro* dissolution behavior can translate into any difference in *in vivo* pharmacokinetics for generic nifedipine ER tablets based on a matrix design can only be evaluated in subjects with an elevated gastric pH. Additional regulatory requirements in this category of oral drug products may be warranted if such changes in PK profiles as a result of pH-dependent dissolution behaviors for matrix-based nifedipine ER tablets could affect the efficacy and safety profiles. Due to complicated release mechanisms, quality attribute profiles, and *in vivo* pharmacokinetic behaviors of ER products, FDA is assessing the need of a drug-drug interaction study between PPIs/antacids (e.g. omeprazole/sodium bicarbonate) and generic nifedipine ER products based on a formulation design which is different from that of its RLD. In so doing, FDA aims to evaluate formulation dependence of interaction with PPIs/antacids which are known to elevate gastric pH and potentially affect *in vivo* drug release. The study results will help the Agency gain a better understanding of drug-drug interaction between oral

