4.0 STUDY OBJECTIVE

4.1 Study Objective

The objective of this study is to compare pharmacokinetics of nifedipine from both generic Nifedipine oral extended-release tablets, 60 mg and reference listed drug PROCARDIA XL (nifedipine) extended-release tablets, 60 mg when co-administered with or without proton pump inhibitor (PPI)/antacid, omeprazole/sodium bicarbonate capsules 40 mg/1100 mg capsules in healthy males and non-pregnant females under fasting conditions.

The two one-sided t-tests procedure Schuirmann proposed will be used to construct the 90% confidence interval at the $\alpha=0.05$ level of significance for the ratio of geometric mean of PK parameters AUC_t, AUC_{inf} and C_{max}. The limits of the 90% confidence intervals are 80.00%-125.00% which will be used for the statistical hypothesis testing. Therefore, it consists of decomposing the interval hypotheses into two sets of one-sided hypotheses.

For the drug interaction for both test and reference products, the calculated 90% confidence interval (CI) for the ratios of geometric means for AUC_t, AUC_{inf} and C_{max} will be used for the following two PK comparisons to assess if the statistical significance of interaction effect between the product type effect (test or reference) and the effect of co-administrating PPI/antacid is or not.

- Test with PPI (Study Arm C)/Test without PPI (Study Arm A)
- Reference with PPI (Study Arm D)/Reference without PPI (Study Arm B)

Hypothesis 1.1: The hypotheses for testing of the interaction effect between Test product and the effect of co-administrating PPI/antacid are as follows:

- The null hypothesis (H01): there is statistical significance of the interaction effect if the 90% CI of the ratios of geometric means for AUC_t, AUC_{inf} and C_{max} is less than 80.00%.
- The alternative hypothesis (H11): there is no statistical significance of the interaction effect if the 90% CI of the ratios of geometric means for AUC_t, AUC_{inf} and C_{max} is greater than or equal to 80.00%.
- The null hypothesis (H02): there is statistical significance of the interaction effect if the 90% CI of the ratios of geometric means for AUC_t, AUC_{inf} and C_{max} is greater than 125.00%.

- The alternative hypothesis (H12): there is no statistical significance of the interaction effect if the 90% CI of the ratios of geometric means for AUC_t, AUC_{inf} and C_{max} is less than or equal to 125.00%.

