Hypothesis 1.2: The hypotheses for testing of the interaction effect between Reference product and the effect of co-administrating PPI/antacid are as follows:

- The null hypothesis (H03): there is statistical significance of the interaction effect if the 90% CI of the ratios of geometric means for AUC_t, AUC_{inf} and C_{max} is less than 80.00%.
- The alternative hypothesis (H13): there is no statistical significance of the interaction effect if the 90% CI of the ratios of geometric means for AUC_t, AUC_{inf} and C_{max} is greater than or equal to 80.00%.
- The null hypothesis (H04): there is statistical significance of the interaction effect if the 90% CI of the ratios of geometric means for AUC_t, AUC_{inf} and C_{max} is greater than 125.00%.
- The alternative hypothesis (H14): there is no statistical significance of the interaction effect if the 90% CI of the ratios of geometric means for AUC_t, AUC_{inf} and C_{max} is less than or equal to 125.00%.

For the relative bioavailability between test and reference products under different conditions (with or without PPI), the calculated 90% confidence interval (CI) for the ratios of geometric means for AUC_t, AUC_{inf} and C_{max} will be used for the following two PK comparisons to assess if the relative bioavailability is or not.

- Test with PPI (Study Arm C)/Reference with PPI (Study Arm D)
- Test without PPI (Study Arm A)/Reference without PPI (Study Arm B) →
Although the generic applicant has already confirmed the bioequivalence between Test and Reference in the absence of PPI, this study will confirm this result.

Hypothesis 2.1: The hypotheses for the assessment of relative bioavailability for Test product with and without PPI are as follows:

- The null hypothesis (H01): there is no comparable bioavailability if the 90% CI of the ratios of geometric means for AUC_t, AUC_{inf} and C_{max} is less than 80.00%.
- The alternative hypothesis (H11): there is comparable bioavailability if the 90% CI of the ratios of geometric means for AUC_t, AUC_{inf} and C_{max} is greater than or equal to 80.00%.
- The null hypothesis (H02): there is no comparable bioavailability if the 90% CI of the ratios of geometric means for AUC_t, AUC_{inf} and C_{max} is greater than 125.00%.

- The alternative hypothesis (H12): there is comparable bioavailability if the 90% CI of the ratios of geometric means for AUC_t, AUC_{inf} and C_{max} is less than or equal to 125.00%.

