Hypothesis 2.2: The hypotheses for the assessment of relative bioavailability for Reference product with and without PPI are as follows:

- The null hypothesis (H03): there is no comparable bioavailability if the 90% CI of the ratios of geometric means for AUC_t, AUC_{inf} and C_{max} is less than 80.00%.
- The alternative hypothesis (H13): there is comparable bioavailability if the 90% CI of the ratios of geometric means for AUC_t, AUC_{inf} and C_{max} is greater than or equal to 80.00%.
- The null hypothesis (H04): there is no comparable bioavailability if the 90% CI of the ratios of geometric means for AUC_t, AUC_{inf} and C_{max} is greater than 125.00%.
- The alternative hypothesis (H14): there is comparable bioavailability if the 90% CI of the ratios of geometric means for AUC_t, AUC_{inf} and C_{max} is less than or equal to 125.00%.

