13.3.3 Statistical Analysis

Descriptive statistics (min, max, median, mean, standard deviation and coefficient of variability) of all PK parameters will be provided for nifedipine for all study arm groups.

ANOVA including sequence, subjects nested within sequence, period and study arm will be performed on the ln-transformed data for AUC_t , AUC_{inf} and C_{max} and on the untransformed data for T_{max} , λ and $T_{1/2}$.

T_{max} will be analyzed using an additional non-parametric test (Wilcoxon test).

The 90% CI of the ratios of geometric means for AUC_t , AUC_{inf} and C_{max} will be calculated based on the LSMEANS and ESTIMATE of the ANOVA.

The following PK comparisons will be carried out:

- Test with PPI (Study arm C)/Test without PPI (Study arm A)
- Reference with PPI (Study arm D)/Reference without PPI (Study arm B)
- Test with PPI (Study arm C)/Reference with PPI (Study arm D)
- Test without PPI (Study arm A)/Reference without PPI (Study arm B)

For Pharmacodynamic Data:

The descriptive statistics (min, max, median, mean, standard deviation and coefficient of variability) of the gastric pH and change of gastric pH will be calculated for both test and reference products.

Analysis of Variance (ANOVA) for gastric pH and change of gastric pH from baseline will be carried out.

The following gastric pH comparisons will be carried out:

- Study arm C PPI (Day7) – Study arm A (Day2)

- Study arm D_{PPI (Day7)} – Study arm B_(Day2)
- The comparison of the change between test and reference can be assessed

Additional statistical and alternate tests will be performed if necessary.

Missing data will not be included in the statistical analysis. There are potential two kinds of unbalanced designs for the analysis: (1) unequal number of subjects across groups, (2) missing cells: there are not available data for some subjects. The Type 3 method will be used for the calculation of sums of squares using SAS software. All the fixed effects will be tested using the Type 3 in the ANOVA to detect statistically significant differences ($\alpha=0.05$) if applicable. A mixed effects ANOVA model for gastric pH with fixed factors of sequence, period, and study arm and random effects of subject will be fit. A compound-symmetric or other appropriate covariance structure will be used in the analysis.

The null hypotheses for gastric pH comparisons for different study arms are:

- For the comparison of Study Arm A and Study Arm C

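### The product-by-PPI interaction named in section 4.1 has no planned PK contrast or confidence interval; separate within-product equivalence verdicts stand in for it and are mislabelled

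*Combined protocol and SAP*

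**What the plan says.** Section 4.1 assigns the intervals for C/A and D/B the task "to assess if the statistical significance of interaction effect between the product type effect (test or reference) and the effect of co-administrating PPI/antacid". Section 3.1 gives the same purpose: "FDA aims to evaluate formulation dependence of interaction with PPIs/antacids".

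The method is equivalence testing: "The two one-sided t-tests procedure Schuirmann proposed will be used to construct the 90% confidence interval", and "The limits of the 90% confidence intervals are 80.00%-125.00"%. Hypothesis 1.1 applies this to the test product and Hypothesis 1.2 to the reference. In both, the null hypothesis is worded as a statistically significant interaction and the alternative as none.

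Section 13.3.3 fits an ANOVA with sequence, subject within sequence, period and a four-level study-arm term. Under "The following PK comparisons will be carried out" it lists C/A, D/B, C/D and A/B only. A comparison of the change between test and reference appears there for gastric pH alone, and as an option.

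Section 4.1 then introduces relative bioavailability of test against reference, naming C/D and A/B, but the hypotheses that follow are headed otherwise: "Hypothesis 2.1: The hypotheses for the assessment of relative bioavailability for Test product with and without PPI are as follows" and "Hypothesis 2.2: The hypotheses for the assessment of relative bioavailability for Reference product with and without PPI are as follows".

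**The concern.** Whether a PPI effect depends on formulation is a between-product question. C/A is the PPI effect in the test product and D/B the PPI effect in the reference; neither is an interaction between product and PPI. Three problems follow.

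- Failing to reject the null of an equivalence test means that equivalence was not shown. It is not evidence of an effect, still less of a significant one.
- One pass and one fail does not show that the products differ, and two passes do not show that they respond alike.
- The headings of Hypotheses 2.1 and 2.2 repeat the within-product comparisons, so C versus D and A versus B have no correctly headed hypothesis.

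At stake is the sentence the report will carry. A PPI interaction for the generic and none for the brand could be reported when the PPI effect is the same in both, or no interaction for either when the two products move in opposite directions.

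**Working it through.** **Inputs.** From section 7.1: intra-subject CV 27%, geometric mean ratio 1.08, limits 80-125%, at least 80% power, at least 52 completers of 65-66 enrolled. From section 4.1: two one-sided tests at 0.05. Assumptions added here: one PK metric, equal within-subject variance in all arms, independent within-subject errors, balanced and complete four-period data. The n = 66 results suppose that every enrolled subject completes.

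**The plan's own figure.** Log-scale SD = √ln(1 + 0.27²) = 0.2653. For one 2x2 comparison with true ratio 1.08, 44 subjects give 80% power (81.5%), and 52 completers give 87%. The stated power of at least 80% therefore holds, for a single test-versus-reference ratio.

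**Precision.** Residual df = 3n − 6, which is 150 at n = 52; t(0.95) = 1.655.

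- One ratio: SE = 0.2653 × √(2/52) = 0.0520; 90% CI factor = exp(1.655 × 0.0520) = 1.090.
- Ratio of ratios, (C−A)−(D−B) on the log scale: SE = 0.2653 × √(4/52) = 0.0736; 90% CI factor = exp(1.655 × 0.0736) = 1.13. At n = 66 it is 1.114.
- If the CV were 20% to 35% (an assumed range), the factor at n = 52 would run from 1.095 to 1.169.

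**Verdicts when there is no product-by-PPI interaction** (same true PPI ratio in both products; 400,000 simulated trials per row):

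| True C/A = D/B | Verdicts disagree, n = 52 | n = 66 |
|---|---|---|
| 1.00 | 1.7% | 0.3% |
| 1.05 | 9% | 3% |
| 1.08 | 22% | 12% |
| 1.15 | 50% | 49% |

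Hand check: at 1.08 and n = 52 each verdict passes with probability 0.876. The two ratios share no arm, so disagreement is close to 2 × 0.876 × 0.124 = 0.217.

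**Verdicts when there is an interaction.** With C/A = 1.08 and D/B = 1/1.08, the ratio of ratios is 1.08² = 1.17. Both verdicts pass in 0.876² = 77% of trials at n = 52, and in 87% at n = 66. Two true ratios inside the limits are compatible with a ratio of ratios as large as 1.25/0.80 = 1.5625.

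**What the missing contrast could detect** (two-sided 5% test, n = 52 / n = 66):

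- Ratio of ratios 1.15: ln(1.15)/0.0736 = 1.90 standard errors at n = 52; power 47% / 57%.
- Ratio of ratios 1.20: ln(1.20)/0.0736 = 2.48 standard errors at n = 52; power 69% / 79%.

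**The case against.** The strongest reply is that interaction here means a drug-drug interaction within each product. The title calls the trial a drug-drug interaction study, and Hypotheses 1.1 and 1.2 each take one product. On that reading C/A and D/B against 80-125% are proper no-effect tests. That much stands. But the sentence in section 4.1 names product type as one of the two interacting factors, section 3.1 speaks of formulation dependence, and calling failed equivalence a significant interaction is wrong on either reading.

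A reader might infer that the trial cannot compare the products at all. The documents do not support this. C/D addresses the question in section 3.1 of whether the products remain bioequivalent at raised gastric pH, and A/B anchors it. With no interaction and an assumed true A/B of 1, C/D passes in 99% of simulated trials at n = 52. In the opposite-direction case (1.08 and 1/1.08) it passes in only 37%, which would warn the reader; but if A/B were 1/1.08 it would pass in 88%. C/D and A/B are again two separate verdicts, so they answer the interaction question only in part.

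A reader might also infer that chance disagreement is generally large. It is not: it is negligible near a ratio of 1.00 and grows as the common ratio approaches the limit. Nor is it an error if both products fail at a true ratio of 1.26. That value lies outside 80-125%, so both failing (93% at n = 52) is the correct within-product verdict. The background figures, "AUC and C_{max} of nifedipine after pretreatment with omeprazole 20 mg once daily for 8 days were 1.26 and 0.87 times" those after placebo, concern an immediate-release tablet and include a Cmax ratio inside the limits. They make a PPI effect common to both products plausible, no more.

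Finally, the planned ANOVA already makes the contrast estimable, and a point estimate follows by dividing the reported ratios. What the plan lacks is the interval and a rule for reading it. The allowance in 13.3.3 for further tests if needed commits to neither.

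**Conclusion.** Wrong as written. The plan names a product-by-PPI interaction, plans no PK contrast or interval for it, and gives failed equivalence the label of a significant interaction. The headings of Hypotheses 2.1 and 2.2 contradict the comparisons listed directly above them; the comparisons themselves are named correctly there and in 13.3.3, so the planned C/D and A/B analyses are not in doubt.

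The practical size depends on the true PPI ratio: little is lost if it is near 1.00 in both products, while from about 1.08 upward the pair of verdicts becomes an unreliable guide to a product difference. The percentages rest on the stated CV and the simplifying assumptions listed with the calculation. The faults in the labels and the absence of the contrast rest on the text alone.

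This does not show that the sample size is wrong for its stated purpose. It does mean that the trial was not sized for the interaction.

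**What to change.** 1. In 13.3.3, add the ESTIMATE contrast (C−A)−(D−B) from the planned ANOVA for ln AUCt, ln AUCinf and ln Cmax. Report the back-transformed ratio of ratios with its 90% CI as the estimate of product-by-PPI interaction.
2. State in advance how it will be read: for example, as an estimate with no equivalence claim, or as evidence of interaction if the interval excludes 1. Excluding 1 from a 90% CI is a two-sided 10% test, whereas the power figures above are for a two-sided 5% test, so the level should be named. The documents set no margin for the ratio of ratios, and none is needed if no equivalence claim is made.
3. State that the trial was not sized for this contrast, and give its power.
4. Relabel Hypotheses 1.1 and 1.2 as the PPI effect within product, with the outcome worded as absence of a relevant PPI effect shown or not shown.
5. Rewrite Hypothesis 2.1 as C versus D and Hypothesis 2.2 as A versus B, in terms of the true geometric mean ratios rather than the position of the interval.

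The cost is wording, one extra analysis line per parameter, and an interval with a standard error √2 times that of a single ratio. No new data or subjects are required.

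### Section 4.1 heads Hypotheses 2.1 and 2.2 with the wrong contrasts and labels the equivalence null a significant interaction, leaving intervals that cross 80-125% mislabelled or without a conclusion

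*Combined protocol and SAP*

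**What the plan says.** Section 4.1 sets a common rule: "The two one-sided t-tests procedure Schuirmann proposed will be used to construct the 90% confidence interval", and "The limits of the 90% confidence intervals are 80.00%-125.00% which will be used for the statistical hypothesis testing". Two pairs of hypotheses follow.

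- **First pair (1.1, 1.2).** The stated purpose is to assess "the statistical significance of interaction effect between the product type effect (test or reference) and the effect of co-administrating PPI/antacid". The ratios listed are C/A and D/B. Each null reads "there is statistical significance of the interaction effect if the 90% CI of the ratios of geometric means" for AUCt, AUCinf and Cmax lies below 80.00% (or, in the second one-sided null, above 125.00%). The alternatives are worded as no statistical significance of the interaction effect.
- **Second pair (2.1, 2.2).** The lead-in concerns relative bioavailability between the two products, with or without PPI. It lists C/D ("Test with PPI (Study Arm C)/Reference with PPI (Study Arm D") and A/B. The hypotheses beneath are headed "Hypothesis 2.1: The hypotheses for the assessment of relative bioavailability for Test product with and without PPI are as follows" and "Hypothesis 2.2: The hypotheses for the assessment of relative bioavailability for Reference product with and without PPI are as follows".

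Section 13.3.3 lists all four ratios (C/A, D/B, C/D, A/B). Section 7.1 sizes the study for Test versus Reference against 80-125%.

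**The concern.** There are two separate defects.

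First, the headings of 2.1 and 2.2 contradict the comparisons listed directly above them. Taken at face value, C/A and D/B each have two hypotheses with differently named conclusions (interaction, and comparable bioavailability), while C/D and A/B have none. C/D is the comparison that answers the question in Section 3.1, whether the products remain bioequivalent at raised gastric pH.

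Second, in a two one-sided tests procedure the null is that the true ratio lies outside the margin. Failing to reject it means equivalence was not shown; it is not a finding of interaction. Here the null is a statement about the interval, which is a sample quantity, and carries the label of a significant interaction. The label is also wrong for the estimand: C/A and D/B are within-product PPI effects, whereas an interaction between product and PPI is the ratio of the two.

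The results are meant to inform regulatory standards for this class of product, and Section 13.3 lets analyses be altered with justification. An ambiguous conclusion rule could therefore be settled after the data are seen.

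**Working it through.** **Headings against listed comparisons (Section 4.1)**

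| Item | Contrasts |
|---|---|
| List before Hypotheses 1.1/1.2 | C/A, D/B |
| Headings of 1.1/1.2 | C/A, D/B |
| List before Hypotheses 2.1/2.2 | C/D, A/B |
| Headings of 2.1/2.2 | C/A, D/B |

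Only the last row is out of place. The text under 2.1 and 2.2 (comparable bioavailability, 80.00%, 125.00%) fits C/D and A/B without change.

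**Inputs.** From Section 7.1: CV 27%, ratio 1.08, at least 52 completers, power at least 80%. From Section 4.1: one-sided alpha 0.05, limits 0.80 and 1.25. Section 7.1 gives the CV for Test versus Reference; applying it to C/A and D/B is an assumption. All results are for one metric at a time.

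**Formulas.**
- Log-scale within-subject SD: sqrt(ln(1 + 0.27²)) = 0.2653.
- SE of a pairwise log ratio: 0.2653 × sqrt(2/52) = 0.0520.
- Residual df of the four-period ANOVA: 3 × 52 − 6 = 150, so t(0.95) = 1.655.
- 90% CI: estimate ×/÷ exp(1.655 × 0.0520) = ×/÷ 1.090.
- Power is integrated over the chi-square distribution of the residual variance.

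**The plan's own figure.** At a ratio of 1.08 and n = 52, power is 87.0% with 50 df (2x2) and 87.5% with 150 df. The stated minimum of 80% is met.

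**Where C/A or D/B intervals would fall (n = 52, 150 df)**

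| True ratio | CI not contained in 80-125% | CI wholly outside |
|---|---|---|
| 1.08 | 12% | below 0.01% |
| 1.10 | 21% | below 0.01% |
| 1.15 | 52% | 0.06% |
| 1.20 | 81% | 0.8% |

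So nearly every interval that fails crosses the limit. The wording can be read in two ways:
- If failing the two one-sided tests triggers the label, a crossing interval is reported as a significant interaction.
- If the whole interval must lie beyond the limit, a crossing interval satisfies neither the null nor the alternative and has no stated conclusion.

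**Relation to a ratio of 1.** At the planned precision, equivalence passes for observed ratios from 0.872 to 1.147. A ratio differs from 1 (two-sided 0.05) above 1.108 or below 0.902. Between 1.108 and 1.147 the label misleads the other way: an observed 1.12 has 90% CI 1.028 to 1.221, which excludes 1, yet it would be called not statistically significant.

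**Relation to a product-by-PPI interaction.** The log of (C/A)/(D/B) has SE 0.2653 × sqrt(4/52) = 0.0736, so its 90% CI is ×/÷ 1.129.
- C/A = D/B = 1.20: each interval is 1.101 to 1.308 and crosses 1.25. The ratio of ratios is 1.00 (0.885 to 1.129), so no interaction is indicated.
- C/A = 0.88 (0.807 to 0.959) and D/B = 1.14 (1.046 to 1.243): both pass, and both would be called no interaction. The ratio of ratios is 0.772 (0.683 to 0.872), which excludes 1.

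**The case against.** The strongest reply is that nothing computed changes. Section 4.1 sets the 90% interval and the 80-125% limits for the whole section and lists C/D and A/B as comparisons to be assessed with them. Section 13.3.3 lists them again, and Section 7.1 sizes the study for them. That stands. A reader might infer from the wrong headings that C/D has no decision rule; the documents do not support this. What it lacks is a correctly headed hypothesis.

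A reader might also take the 12% to 81% figures as rates of false interaction findings. The documents do not support that either, for two reasons. The figures attach to the interaction label only if failing equivalence triggers it; read literally, as the whole interval lying beyond a limit, the label would apply in at most 0.8% of trials at these ratios. And at a CV of 27%, essentially every interval that fails also differs from 1; failing without differing from 1 at the two-sided 0.05 level would need a CV above about 32% with 52 completers. The intervals are inconclusive about the limits, not about whether any PPI effect exists.

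Neither reply rescues the text. The headings still contradict the list, and a crossing interval gets a wrong conclusion on one reading and none on the other.

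**Conclusion.** The point holds as a defect in the stated hypotheses and conclusions, not in the planned computations. Two headings name the wrong contrasts. The nulls of 1.1 and 1.2 are put on the interval instead of the true ratio, and their label is wrong both for an equivalence test and for the within-product ratios it is attached to.

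The outcome affected is not rare if the PPI has a moderate effect: about 12%, 21%, 52% and 81% of trials at true ratios of 1.08, 1.10, 1.15 and 1.20, nearly all with intervals that cross a limit. These figures rest on 52 completers, 150 df and a 27% CV carried over from the Test/Reference assumption. If the true ratio is 1.00, only about 0.9% of trials fail. The contradiction in the headings and the gap in the conclusion rule do not depend on any of these numbers.

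**What to change.** In Section 4.1:

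1. Head Hypothesis 2.1 as C/D (Test with PPI versus Reference with PPI) and 2.2 as A/B (both without PPI).
2. State every null on the true geometric mean ratio: ratio ≤ 0.80 or ratio ≥ 1.25, with the alternative 0.80 < ratio < 1.25.
3. For C/A and D/B, replace the significance wording with three outcomes: *no PPI effect beyond 80-125% shown* (CI inside the limits); *effect beyond the limits shown* (CI wholly outside); *inconclusive as to the 80-125% limits* (CI crosses a limit).
4. Describe C/A and D/B as within-product PPI effects. If a product-by-PPI interaction is to be claimed, report (C/A)/(D/B) with its 90% CI from the same ANOVA.

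The cost is wording, plus one extra contrast if item 4 is taken up. Margins, alpha and sample size stay as they are. The downside is that some results that would have been called interactions become inconclusive. The ratio of ratios is also less precise than a pairwise ratio (×/÷ 1.129 against ×/÷ 1.090 at 52 completers).
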